### 6.4 STUDY INTERVENTION COMPLIANCE

This study is a survey. Thus, as long as the participant completes the assigned survey, they will have adhered to the study protocol.

### 6.5 CONCOMITANT THERAPY

N/A

#### 6.5.1 RESCUE MEDICINE

N/A

### 7 STUDY INTERVENTION DISCONTINUATION AND PARTICIPANT DISCONTINUATION/WITHDRAWAL

## 7.1 DISCONTINUATION OF STUDY INTERVENTION

Participant responses will be monitored for concerning responses. If there are repeated concerning responses about the survey or intervention, the study will be discontinued. Participants can also stop participating in the survey at any time.

## 7.2 PARTICIPANT DISCONTINUATION/WITHDRAWAL FROM THE STUDY

Participants are free to withdraw from participation in the study at any time upon request.

An investigator may discontinue or withdraw a participant from the study for the following reasons:

- Participant does not complete the intervention within the designated time frame

The reason for participant discontinuation or withdrawal from the study will be recorded on the Master Participant list. Subjects who sign the informed consent form and are randomized but do not receive the study intervention may be replaced. Subjects who sign the informed consent form, and are randomized and receive the study intervention, and subsequently withdraw, or are withdrawn or discontinued from the study, will be replaced.

## 7.3 LOST TO FOLLOW-UP

A participant will be considered lost to follow-up if he or she fails to complete the survey within the specified time frame and is unable to be contacted by the study site staff.

The following actions must be taken if a participant fails to complete the survey:

- The site will attempt to contact the participant via email with a survey reminder and ascertain if the participant wishes to and/or should continue in the study.
- Before a participant is deemed lost to follow-up, the investigator or designee will make at least two emails to the participant. These contact attempts should be documented in the participant's medical record or study file.
- Should the participant continue to be unreachable, he or she will be considered to have withdrawn from the study with a primary reason of lost to follow-up.

# 8 STUDY ASSESSMENTS AND PROCEDURES

## 8.1 EFFICACY ASSESSMENTS

To test intervention efficacy, the participant will be asked to answer a set of clinical questions after reading the case study. They will first do this without the intervention and then read another case study using the intervention. This will be administered through Qualtrics in survey form.

The questions include:

- Would you recommend feeding therapy to this child? Yes/No
  - If yes, "With what frequency would you recommend therapy?"
    - 2 times per week, 1 time per week, Less than one time per week
  - If yes, "What therapy target areas might you include for this child?" (select all that apply)

- Oral motor skills, sensory, behavioral, medication, modification of food/liquid, modification of equipment (seating, utensils, etc.), modification of environment (location, distractions, routine, etc), parent coaching, other (fill in)
- If yes, "What would be the recommended length of treatment for this child?"
  - Less than 6 months, 6-12 months, More than 12 months
- What diagnosis would you give this child?
- Would you refer this family to any other providers/specialists for evaluation/treatment? Yes/No
  - If yes, "What other professionals would you refer this child to? Check all that apply."
    - Nutritionist/dietician, gastroenterologist, otolaryngologist (ENT), aerodigestive clinic, pulmonologist, occupational therapist, speech language pathologist, psychologist/social worker, applied behavior analyst (ABA), allergist, multidisciplinary feeding team, other (list)

In addition to the clinical questions, the following questions will be asked in order for the participant to evaluate the tool:

- With a likert scale of completely agree, agree, neither agree nor disagree, disagree, completely disagree
  - The Clinical Feeding Guide meets my approval
  - The Clinical Feeding Guide is appealing to me
  - I like the Clinical Feeding Guide
  - I welcome the Clinical Feeding Guide
  - The Clinical Feeding Guide seems fitting
  - The Clinical Feeding Guide seems suitable
  - The Clinical Feeding Guide seems applicable
  - The Clinical Feeding Guide seems like a good match
  - The Clinical Feeding Guide seems implementable
  - The Clinical Feeding Guide seems possible
  - The Clinical Feeding Guide seems doable
  - The Clinical Feeding Guide seems easy to use
- If you could make changes to the CFG you would (check all that apply):
  - Make it shorter, make it longer/more comprehensive, change the format, add items, remove items, I wouldn't make any changes, I wouldn't use it
- Please list 1-2 strengths of the CFG
- Please list 1-2 changes you would make to the CFG to make it more useful for clinical practice
- I would use the CFG in clinical practice (5pt likert scale from strongly agree to strongly disagree)
  - If Strongly, somewhat, or neither agree/disagree is selected: "Please describe why you would use the CFG in clinical practice"
  - If somewhat disagree, strongly disagree or neither agree/disagree is selected: "Please describe why you would not use the CFG in clinical practice"

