## 2.3 RISK/BENEFIT ASSESSMENT

### 2.3.1 KNOWN POTENTIAL RISKS

There are no known risks of using the intervention, as it is being used on mock case studies. There is the potential for participants to experience emotional distress or consequences of a breach of confidentiality. Although the likelihood of a breach of confidentiality is low, the data collected could yield information about participants' behaviors and demographics that could cause emotional distress if confidentiality were breached. Professionals may also experience fatigue, frustration, or stress will reading case studies. However mock case studies have been determined to yield the least stress over considering real cases or viewing videos of real children.

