## 4 STUDY DESIGN

### 4.1 OVERALL DESIGN

This is a randomized crossover pilot study. It will be conducted online through one site, UNC Chapel Hill. The study intervention is the 'Clinical Feeding Tool' also known as the decision support tool. Our hypothesis is that clinicians will change their recommendations for feeding therapy and specialist referral when using the tool compared to when they do not use the tool. Clinicians will be randomly assigned to respond to either Case A or Case B without using the tool (2 groups). Then, they will respond to the other case using the tool. Total participation time is estimated at 20 minutes.

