### 4.2 SCIENTIFIC RATIONALE FOR STUDY DESIGN

We have selected a crossover design for this pilot study in order to directly compare use of the tool to no use of the tool among a small group of participants. Therefore, participants will serve as their own control group. This was chosen given the varying experience of the participants with feeding.

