### 4.3 JUSTIFICATION FOR DOSE

All therapists will view the full tool in the survey in order to directly compare use of the tool to no use of the tool.

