### 6.3 MEASURES TO MINIMIZE BIAS: RANDOMIZATION AND BLINDING

14 OTs and 14 SLPs will receive case A first; 14 OTs and 14 SLPs will receive case B first. There are two versions of the survey – one where case A is presented first and one where case B is presented first. Providers will be sent the link to the version to which they are assigned.

Assignment will be based on the order of study entry. For example, the first SLP to enroll will receive case A first, the second SLP to enroll will receive case B first, etc. Similarly, the first OT to enroll will receive case A first, the second OT to enroll will receive case B first, etc.

The PI will complete all randomization computations. There will not be blinding. Blinding is considered unnecessary in this case because the researchers will not have direct interaction with participants, participants will complete the full survey and intervention independently without interaction with the researchers.

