## 9.2 SAMPLE SIZE DETERMINATION

This is a pilot study. Sample size was selected based on available funding and to achieve equal numbers in each group (group 1: case A then case B; group 2: case B then case A) as well as equal numbers of SLPs and OTs per group (group 1: 14 SLP, 14 OT. Group 2: 14 SLP, 14 OT).

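### The tool is always used on the second case, so the concordance endpoints estimate the joint effect of tool and second position, yet the plan presents them as a direct tool comparison

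*Combined protocol and SAP*

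**What the plan says.** Section 4.1 describes the design in these words: "This is a randomized crossover pilot study". Each therapist is assigned Case A or Case B to answer without the tool, and the section continues: "Then, they will respond to the other case using the tool". Section 8.1 gives the same sequence for the assessments: "They will first do this without the intervention and then read another case study using the intervention".

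Only the case order varies. Section 6.3 describes two survey versions, "one where case A is presented first and one where case B is presented first", and section 9.2 defines the groups as "group 1: case A then case B; group 2: case B then case A", with 28 therapists in each. No version puts the tool first.

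The stated purpose is a comparison of tool with no tool. Section 4.2 reads "We have selected a crossover design for this pilot study in order to directly compare use of the tool" and adds that participants act as their own controls. Section 4.3 repeats the aim: "in order to directly compare use of the tool to no use of the tool". The objectives (1.1, 3), the hypotheses (9.1) and the analyses (9.4.2, 9.4.3) all state the contrast as using against not using the tool.

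Sections 9.4.2 and 9.4.3 analyse each case separately, descriptively. A chi-square test is added for the yes/no and frequency endpoints if its assumptions are met. The covariates to be considered (9.4.1) are years of experience and profession. No section mentions order or carry-over, gives a reason for the fixed order, or states a limitation on this account.

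**The concern.** A reader expects a crossover to vary the order of the conditions, so that order can be separated from treatment. Here the cases are counterbalanced but the conditions are not. Counterbalancing deals with one case being harder than the other. It does nothing about the second case being answered after practice, after fatigue, or after the same therapy and referral questions have just been worked through once.

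At stake is what the concordance results can be said to show. If they are reported as the plan words them, the tool would be credited with, or denied, a difference that belongs to tool and second position together. This holds for descriptive percentages as much as for p-values, so it includes the third primary endpoint (specific specialist referrals), which is descriptive only. The order could also hide a tool effect if the two work in opposite directions.

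The plan gives no evidence on how large an order effect might be. Section 2.3.1 does allow that "Professionals may also experience fatigue, frustration, or stress will reading case studies", but it lists this as a burden on participants, not as a finding about their answers.

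**Working it through.** **1. Layout.** The sample size is 2 × (14 + 14) = 56, as section 9.2 states. The sequences in 4.1, 6.3, 8.1 and 9.2 produce four cells:

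| Group | Case | Position | Tool |
|---|---|---|---|
| 1 (n = 28) | A | first | no |
| 1 (n = 28) | B | second | yes |
| 2 (n = 28) | B | first | no |
| 2 (n = 28) | A | second | yes |

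In every row, tool = yes exactly when position = second. Their correlation is 1.

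**2. What the contrast estimates.** Write the expected response as m(case) + T if the tool is used + P if the case is read second.

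- Case A: group 2 minus group 1 = (m(A) + T + P) − m(A) = T + P.
- Case B: group 1 minus group 2 = (m(B) + T + P) − m(B) = T + P.
- Within therapist: group 1 gives m(B) − m(A) + T + P and group 2 gives m(A) − m(B) + T + P. Their average is again T + P.

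The design matrix for intercept, case, tool and position has rank 3 of 4. Within either case, intercept, tool and position have rank 2 of 3. Adding the sequence group gives rank 4 of 5. Neither an order term nor the covariates in 9.4.1 can separate T from P.

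The sum T + P is exact only on an additive scale; in general the estimate is the joint effect. For therapy frequency and targets, which are asked only of those who recommend therapy, tool or position can also change who answers.

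**3. Illustration of size.** The documents give no response rates, order effect or alpha, so all three are assumed here. The calculation is an exact enumeration of two binomials, 28 v 28, with an uncorrected two-sided chi-square at 0.05 and T = 0. The statistic is (a/28 − b/28)² / [p(1 − p) × 2/28], with p = (a + b)/56, and it rejects above 3.84.

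| First-position yes rate | Order shift (points) | Rejects |
|---|---|---|
| 60% | 0 | 4.8% |
| 60% | +5 | 6.7% |
| 60% | +10 | 12.4% |
| 60% | +15 | 22.9% |
| 60% | +20 | 38.2% |
| 60% | −10 | 10.9% |
| 60% | −20 | 30.8% |

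Over first-position rates of 40% to 70%, a +10 shift gives 11–14% and a +20 shift gives 31–47%.

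Masking: with a 60% base, a true +20 point tool effect and a −15 point order effect, the comparison is 60% v 65% (60 + 20 − 15). It is detected in 6.7% of trials per case, against 38.2% with no order effect.

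**4. Effect of the plan's condition on the chi-square.** Section 9.4.2 runs the test only if its assumptions hold. Reading that as all expected counts at least 5, which is an assumption, the total of yes answers must lie between 10 and 46 of 56.

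| Rates compared | Test is run | Run and rejects |
|---|---|---|
| 60% v 70% | 99.9% | 12.4% |
| 80% v 90% | 33% | 7.3% |
| 85% v 95% | 5% | 2.0% |
| 90% v 95% | under 1% | 0.2% |

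At high yes rates the false-positive illustration therefore shrinks. The shift in the reported percentages remains.

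**The case against.** The strongest defence is that no-tool-first is a sensible choice. A therapist who has seen the checklist cannot unsee it, and it is also supplied as a PDF (6.2.2), so a tool-first sequence risks carry-over into the no-tool case. That stands as a reason for the order. The plan does not give it, however, and it does not remove the aliasing.

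It can also be said that this is a small, mostly descriptive pilot, sized on funding, with short mock cases and about 20 minutes of participation. That limits the consequences and makes a large fatigue effect less obvious. It does not change what the percentages estimate, and section 9.1 still sets out hypotheses about the tool.

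A reader might infer that nothing can be credited to the tool unless the order effect is exactly zero. That goes too far. An order effect that is small relative to the observed difference would leave room for a qualified attribution. For the specialist endpoint, a shift confined to the disciplines behind the checklist's four headings would be harder to explain by practice or fatigue. Such a pattern would be supporting evidence, but it does not separate the two effects.

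A reader might also take the rejection rates above as this trial's error rates. They are not, because every input to them is assumed.

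**Conclusion.** The point holds as a mismatch between the design and the claims made for it. Tool and second position coincide completely, so the three primary and two secondary concordance endpoints estimate their joint effect. This follows from the layout alone and needs no assumption about effect size. The crossover label, the promise of a direct comparison and the statement that participants are their own controls each claim a property that the planned per-case comparison lacks.

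The amount of bias is unknown and may be negligible. The illustrative 12% and 38% rejection rates rest on an assumed 60% yes rate, alpha of 0.05, no tool effect and the chi-square being run. The documents support neither the presence nor the absence of an order shift. They do not support the inference that a positive result would be an artefact, or that the pilot has to be redesigned. The acceptability, appropriateness and feasibility scores are rated once, after tool use and with no comparator, and are untouched.

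**What to change.** Change the wording and the conclusion:

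1. In 4.1 and 4.2, replace the crossover label with *fixed-order (no tool, then tool) design with counterbalanced cases*. In 4.2, correct the statement about participants being their own controls, since the per-case comparison is between different therapists. How the allocation itself is described is a separate matter.
2. In 1.1, 3, 9.1, 9.4.2 and 9.4.3, define the concordance contrast as *within each case, therapists reading it second with the tool v therapists reading it first without the tool*.
3. In 4.2 and 4.3, qualify the direct comparison with *assuming no material order effect*. In 4.1 and 9.4, add: *Tool use and order coincide in this design. The concordance results estimate their joint effect and cannot by themselves be attributed to the tool; attribution assumes that any order effect is negligible relative to the observed difference.* Report the concordance results with that limit.

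If avoiding carry-over is the reason for the fixed order, 4.2 is the place to say so.

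The cost is text only, with no new participants, data or analysis. The conclusion becomes more cautious.

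Two redesigns are options for the sponsor to weigh and are not part of the fix. One also varies the tool order; the other adds versions that answer both cases without the tool. At N = 56 either needs four versions of 14, which cuts the clean comparison to 14 v 14 per case. At an assumed 60% v 80%, per-case power is then about 21%, against 38% for 28 v 28, and all expected counts reach 5 in about 31% of trials, against 99%. The first option brings in possible carry-over. The second conflicts with 4.3 and 6.1.2, under which every therapist sees the tool.

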## 8.2 SAFETY AND OTHER ASSESSMENTS

While no obvious safety concerns are expected, provider responses to the survey will be monitored weekly for any concerning responses.

## 8.3 ADVERSE EVENTS AND SERIOUS ADVERSE EVENTS

### 8.3.1 DEFINITION OF ADVERSE EVENTS (AE)

Adverse event means any untoward medical occurrence associated with the use of an intervention in humans, whether or not considered intervention-related (21 CFR 312.32 (a)).

### 8.3.2 DEFINITION OF SERIOUS ADVERSE EVENTS (SAE)

An adverse event (AE) or suspected adverse reaction is considered "serious" if, in the view of either the investigator or sponsor, it results in any of the following outcomes: death, a life-threatening adverse event, inpatient hospitalization or prolongation of existing hospitalization, a persistent or significant incapacity or substantial disruption of the ability to conduct normal life functions, or a congenital anomaly/birth defect. Important medical events that may not result in death, be life-threatening, or require hospitalization may be considered serious when, based upon appropriate medical judgment, they may jeopardize the participant and may require medical or surgical intervention to prevent one of the outcomes listed in this definition. Examples of such medical events include allergic bronchospasm requiring intensive treatment in an emergency room or at home, blood dyscrasias or convulsions that do not result in inpatient hospitalization, or the development of drug dependency or drug abuse.

### 8.3.3 CLASSIFICATION OF AN ADVERSE EVENT

#### 8.3.3.1 SEVERITY OF EVENT

For adverse events (AEs) not included in the protocol defined grading system, the following guidelines will be used to describe severity.

- **Mild** – Events require minimal or no treatment and do not interfere with the participant's daily activities.
- **Moderate** – Events result in a low level of inconvenience or concern with the therapeutic measures. Moderate events may cause some interference with functioning.
- **Severe** – Events interrupt a participant's usual daily activity and may require systemic drug therapy or other treatment. Severe events are usually potentially life-threatening or incapacitating. Of note, the term "severe" does not necessarily equate to "serious".]

#### 8.3.3.2 RELATIONSHIP TO STUDY INTERVENTION

All adverse events (AEs) must have their relationship to study intervention assessed by the PI who communicates with the participant about the concerning survey response and evaluates its relationship with the intervention. The degree of certainty about causality will be graded using the categories below. In a clinical trial, the study product must always be suspect.

- **Related** – The AE is known to occur with the study intervention, there is a reasonable possibility that the study intervention caused the AE, or there is a temporal relationship between the study intervention and event. Reasonable possibility means that there is evidence to suggest a causal relationship between the study intervention and the AE.
- **Not Related** – There is not a reasonable possibility that the administration of the study intervention caused the event, there is no temporal relationship between the study intervention and event onset, or an alternate etiology has been established.

#### 8.3.3.3 EXPECTEDNESS

The PI will be responsible for determining whether an adverse event (AE) is expected or unexpected. An AE will be considered unexpected if the nature, severity, or frequency of the event is not consistent with the risk information previously described for the study intervention.

---

#### 8.3.4 TIME PERIOD AND FREQUENCY FOR EVENT ASSESSMENT AND FOLLOW-UP

The occurrence of an adverse event (AE) or serious adverse event (SAE) may come to the attention of study personnel during weekly review of survey responses.

All AEs will be captured on the appropriate case report form (CRF). Information to be collected includes event description, date and time of survey response, PI's assessment of severity, and relationship to study product. All AEs occurring while on study must be documented appropriately regardless of relationship. All AEs will be followed to adequate resolution.

The PI will record all reportable events with start dates occurring any time after informed consent is obtained until study participation is complete. Events will be followed for outcome information until resolution.

---

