#### 9.4.4 SAFETY ANALYSES

Survey responses will be monitored for any concerns responses and these will be reported.

---

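### Safety reporting relies on weekly review of survey answers, but no question listed in 8.1 asks about the harms named in 2.3.1, so a zero count would be weak evidence of no harm

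*Combined protocol and SAP*

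**What the plan says.** Section 2.3.1 names the foreseeable harms. It states that "There is the potential for participants to experience emotional distress or consequences of a breach of confidentiality" and that "Professionals may also experience fatigue, frustration, or stress" while reading the cases.

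Detection is described in four places, always by the same means:

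- 8.2: "provider responses to the survey will be monitored weekly for any concerning responses". Section 10.1.6 repeats this.
- 8.3.4: adverse and serious adverse events "may come to the attention of study personnel during weekly review of survey responses". The event record holds the "date and time of survey response".
- 8.3.3.2: the relationship to the intervention is "assessed by the PI who communicates with the participant about the concerning survey response".
- 9.4.4, the whole of the safety analysis: "Survey responses will be monitored for any concerns responses and these will be reported".

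Section 8.1 lists the survey questions: clinical questions on the mock case, 12 agreement ratings of the tool, a checklist of possible changes, free text on strengths and changes, intention to use the tool, and free-text reasons for using or not using it. Section 7.2 records reasons for withdrawal on the participant list.

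**The concern.** The harms that 2.3.1 anticipates are felt by the participant. The listed questions concern the mock child or the tool. A participant who was stressed or worn out by the cases would have to say so, unprompted, in a box asking about something else. The safety report in 9.4.4 is drawn from those answers alone, so a clean report could be read as showing that the study did no harm when it shows only that nobody raised the matter.

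Other parts of the protocol depend on the same signal. Section 8.3.4 requires every adverse event on study to be documented. Section 8.3.3.3 judges expectedness partly by frequency. Section 7.1 discontinues the study if concerning responses recur, without defining *concerning* or giving a number. Unprompted remarks give a poor basis for any of these.

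**Working it through.** **Document check.** Each group of questions in 8.1 was compared with the harms in 2.3.1.

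| Content listed in 8.1 | Subject | Asks about the participant's distress, fatigue, frustration or stress? |
|---|---|---|
| Therapy, frequency, targets, length, diagnosis, referral | mock child | no |
| 12 agreement ratings | tool | no |
| Checklist of changes | tool | no |
| Free text: strengths, changes | tool | not asked; could be volunteered |
| Intention to use, with free-text reasons | tool | not asked; could be volunteered |

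Three contacts lie outside the survey answers: withdrawal reasons (7.2), reminder emails to non-completers (7.3) and emailed questions to the investigator at consent (10.1.1.2). None is described as a source of adverse events, and none feeds 9.4.4. The first two reach only people who withdraw or do not finish.

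**Illustration of size.** The plan gives no event rate, detection rate or safety precision, so there is no figure of its own to reproduce.

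- N = 56, from 5.5 and 9.2 (4 cells × 14).
- p = true share of participants with an event. Assumed: 5%, 10%, 20%.
- d = chance that an affected participant volunteers it in the survey. Assumed: 5%, 10%, 25%. For comparison, d = 100% is an idealised limit, not the expected performance of a direct question.

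Treating participants as independent, P(no event recorded) = (1 − p × d)^56.

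| p | Expected true events (56 × p) | d = 5% | d = 10% | d = 25% | d = 100% |
|---|---|---|---|---|---|
| 5% | 2.8 | 87% | 76% | 49% | 5.7% |
| 10% | 5.6 | 76% | 57% | 24% | 0.3% |
| 20% | 11.2 | 57% | 32% | 5.7% | <0.1% |

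Example: p = 10%, d = 5% gives (1 − 0.005)^56 = 0.755.

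**What 0 of 56 would exclude.** The one-sided 95% upper limit on the recorded rate is 1 − 0.05^(1/56) = 5.2%. The limit on the true rate is this divided by d:

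- d = 100%: 5.2%
- d = 25%: 5.2% / 0.25 = 21%
- d = 10%: 5.2% / 0.10 = 52%
- d = 5%: exceeds 100%, so nothing is excluded

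**The case against.** The case for leaving the plan alone has several parts.

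- **The list in 8.1 may not be the whole survey.** It appears under efficacy assessments and is introduced as what the questions include. Demographic items (1.3) and years of experience (9.4.5) are collected but not listed there. This stands: the documents show that no *listed* question asks, not that the survey never asks.
- **Problems could surface elsewhere.** Free text on changes or on reasons not to use the tool could carry frustration, and withdrawal reasons or emails could reveal more. The consent form is not in the text reviewed, so the absence of a contact for reporting problems cannot be asserted. This also stands, but none of these routes is tied to the safety report.
- **Fatigue or frustration may not be an adverse event.** Section 8.3.1 uses a medical definition, and 2.3.1 does not say that these burdens are to be counted. The status is unclear. However, 8.2 and 9.4.4 cover concerning responses generally, so the ambiguity is a reason to state what is counted.
- **The plan claims no incidence and no confidence limit.** True. The figures above show how a zero might be misread; they do not contradict anything the plan states.
- **Risk is low.** Participants are professionals reading mock cases for about 20 minutes, a format chosen to limit stress, and safety is not an endpoint. This limits the importance of the point. Passive review can be defended if its result is described for what it is.

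**Conclusion.** The point holds in a limited form. The only route named for detecting adverse events and reporting safety is review of survey answers, no listed question elicits the harms the protocol itself expects, and withdrawal reasons are not linked to the report. A zero count would therefore be weak evidence of no harm.

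A reader might go further and infer that the survey is incapable of registering these harms, or that the report will show zero whatever happens. The documents do not support that. Free text leaves some chance of detection, and even in the illustration a zero is not certain: at an assumed 10% event rate its probability falls from 76% to 24% as volunteering rises from 5% to 25%. Both rates are assumptions. The qualitative conclusion needs only that volunteering is uncommon.

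No efficacy result is affected. This is a cheap improvement of modest importance.

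**What to change.** 1. **Add one optional closing item to 8.1**, after all endpoint and rating items, asking whether reading the cases or completing the survey caused distress, fatigue, frustration or stress (yes or no, with a text box). Exempt it from the complete-all-items rule in 9.3, 9.4.2 and 9.4.3.
2. **Name the item in 8.3.4 and 9.4.4** and report yes, no and unanswered counts. Use those who answered as the denominator. Show separately those who opened the first case but did not reach the item; counting them as event-free would bring back the false reassurance. Add the withdrawal reasons from 7.2.
3. **Tabulate all yes answers descriptively**, and state how they relate to the definition in 8.3.1 and to concerning responses in 7.1, so that minor burden is not automatically processed as an adverse event.
4. **If no item is added**, have 9.4.4 describe a zero as no events volunteered, not as absence of harm.

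The cost is a few seconds per participant and a few sentences of protocol text. The downside is a few more minor reports for the investigator to assess: at the assumed 10% rate, about six yes answers (56 × 0.10 = 5.6) if everyone affected says so. Without step 3, any of these treated as adverse events would need a case report form and follow-up (8.3.4) and reporting within 3 days (8.3.5). Because the item comes after all endpoint and rating items, it should not influence those answers.
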